associations between postnatal maternal depression and HEU cognitive and executive function^{35,36}. A recent study from Sweden which assessed over 500,000 sibling pairs found that higher birthweight was associated with significantly lower risk of depression, PTSD, ADHD, anxiety and ASD, after controlling for familial confounders³⁷. There is consistent evidence of lower birthweight and poorer growth in HEU compared to HUU^{38,39}. A recent study from Denmark with 485 HEU and 2,495 HUU observed significant growth differences between the groups at birth but differences decreased by 5 years of age⁴⁰. Growth trajectories in HEU may be less compromised among those who receive Option B+ vs. earlier or no PMTCT regimens, and may transition from underweight to overweight during infancy^{41,42, 43}. Using a fetal origins perspective, it is plausible that HEU may have poorer neurodevelopmental and mental health outcomes via fetal exposure to HIV, ART, poor fetal growth, or maternal stress or depression in pregnancy.

Option B+ PMTCT regimen switch from EFZ to DTG may influence HEU outcomes

In 2019, guidelines for ART changed from EFZ-backbone to DTG-backbone regimens, including during pregnancy. Psychiatric symptoms including insomnia, anxiety, depression and suicidality occur with both EFZ and DTG, generally at low prevalence with infrequent discontinuation; since these psychiatric symptoms are markedly increased with HIV infection it is difficult to attribute drug-effects⁴⁴. EFZ was associated with increased suicidal ideation at 12 months postpartum in a cohort of South African women⁴⁵. There is additional evidence that EFZ is associated with mild-moderate neurocognitive impairment, although mechanisms are unclear⁴⁶. Discontinuing EFZ improved sleep quality in a recent randomized trial⁴⁷. DTG administration in pregnancy results in high fetal exposure⁴⁸ and periconceptional DTG was associated with a slightly increased risk of neural tube defects in a large study of 119,033 infants in Botswana⁴⁹⁻⁵¹. In a US multi-site study of 3,747 HEU in the SMART (Surveillance Monitoring for ART Toxicity) cohort, fetal EFZ exposure was associated with increased neurologic conditions (microcephaly, seizures, and eye abnormalities) (Crowell *IDWeek* 2018). There have not been studies to determine long-term outcomes of EFZ and DTG on HEU neuropsychiatric outcomes.

Increased mortality and morbidity in HEU suggest impact of fetal HIV/ART exposure in diverse domains

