Screening for child mental health conditions. The Strengths and Difficulties Questionnaire¹³¹ is a 25-item scale widely used as a screening tool for mental health in numerous LMIC settings¹³², including SSA¹³³. The SDQ will be used beginning at age 3. The SDQ includes 4 difficulty scales (emotional symptoms, conduct problems, hyperactivity/inattention, and peer relationship problems) and a scale for prosocial behavior. The Strengths and Difficulties Questionnaire¹³¹ is a 25-item scale widely used as a screening tool for mental health in numerous LMIC settings¹³², including SSA¹³³. The SDQ will be used beginning at age 3. The SDQ includes 4 difficulty scales (emotional symptoms, conduct problems, hyperactivity/inattention, and peer relationship problems) and a scale for prosocial behavior. SDQ scales had good internal consistency in African studies¹³⁵⁻¹³⁹, although the hyperactivity/inattention scale has performed less well¹³⁸. Poor SDQ scores correlated with expected demographic characteristics in South Africa and Uganda¹³⁷. A z-score corresponding to the 80th-90th and >90th percentiles have been considered borderline and indicative of 'caseness'¹³⁶, and will prompt further screening.

Hearing: We will use combined otoacoustic emission (OAE) and auditory brainstem response (ABR) screening tests to assess hearing. Infants will be screened at 6 weeks using OAE and referred for ABR if they screen positive. At age 3 and 4 years, we will use a smart phone based hearing screen (Hearscreen TM) to assess hearing. These tests are non-invasive and does not involve input of energy into the body.

Summary table for aim 1 data collection

	Enrollment	Month 6	Month 12	Month 18	Month 24	Month 30	Month 36	Month 42	Month 48
Consent	X								
Locator data	X	X	X	X	X	X	X	X	X
Medical history	X	X	X	X	X	X	X	X	X
Anthropometry	X	X	X	X	X	X	X	X	X
MDAT	X	X	X	X	X	X	X	X	X
SDQ							X	X	X
ASD screen				X	X				X
Hearing screen	X						X		X
DBS	X		X		X		X		X

vii. Sample size determination & data analysis

For **all analyses**, *a priori* cofactors of interest in the multivariate analysis include household sociodemographic factors, birthweight, preterm birth, maternal depression, infant sex, maternal education, and infant/child LAZ. Collinearity will be examined using standard error assessments and multivariate models will include non-collinear variables associated with growth in univariate model ($p < 0.05$).

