Mortality, infectious morbidity, and hospitalizations: Cox regression will be used to compare survival of the HEU and HUU cohorts and to determine predictive factors for mortality overall and stratified by HEU/HUU. During the 4-year follow-up period for the aim 1 cohort, incidence of hospitalization, severe pneumonia, and diarrhea will be calculated and compared between HEU and HUU cohorts as number of events over person-time of follow-up with censoring for mortality and loss to follow-up. Predictors of first morbidity (separate analyses for pneumonia, severe diarrhea, and hospitalizations) will be identified using Cox proportional hazards regression with censoring for mortality and loss to follow-up.

Analysis: We will compare MDAT social, motor and language scores and prevalence of ASD between HEU and HUU and among HEU by maternal VL detection in pregnancy, maternal pre-conception ART, and by ART regimen. The percentage of normal, borderline and high scores on the SDQ will be calculated for the domains: emotional problems, conduct problems, hyperactivity, peer problems, and prosocial behavior and for total difficulty. Univariate and multivariate logistic regression will be used to determine whether HEU vs. HUU is associated with higher likelihood of high scores on SDQ domains overall. Among HEU, we will assess influence of maternal VL, ART, and regimen. Multivariate analyses will be adjusted for maternal sociodemographic factors and depression and infant birthweight and growth.

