R33 Aim 2				
Difference in BENC1 scores	0.29	1000 HEU: 100 HUU age stratum (7-11yo)		SD=1.0
Difference in ADHD prev.	7.7%	1000 HEU: 100 HUU		2.7% in HUU ¹⁷⁵
Difference in depression prev	10.1%	1000 HEU: 100 HUU per age stratum		HUU 10%

Analyses: For binary outcomes such as ADHD and depression, multivariate generalized linear models (GLM) with log link and binomial family for relative risk estimation clustered by site will be used. For continuous variables such as NIH-Toolkit, we will use multivariate GLM with Gaussian family and identity link. As previously noted in Aim 1, we will include *a priori* potential confounders - maternal depression, preterm birth, and infant birthweight - in multivariate analysis, after assessment of collinearity.

MDAT (social, fine motor, gross motor, language)	GLM
Hearing	GLM
BENCI (processing speed, visual-motor coordination, attention, language, memory, executive function)	GLM
SDQ total domain score	GLM
ADHD screen (analyze positive SNAP-IV and subset validated on MINI-Kid)	GLM
PHQ-9 (prevalence of moderate-severe symptoms)	GLM
Neuropsychiatric diagnoses	GLM

Training procedures for aim 1 and 2

The study team will develop protocols and training materials for clinic staff. A 5-day training workshop will be designed. The package will include the basics of early childhood development, pediatric mental health, screening and use of the study screening and diagnostic tools. The training will cover neurodevelopmental assessments, psychometric testing, and administration, scoring and interpretation of the MDAT and NIH Toolbox. The 5-day nurse training workshop will cover general sensitization to the testing situation, including ensuring that the child follows the instructions, methods of cross-checking to determine whether a child understood instructions, learning when to give breaks, how to re-engage the child and how to react to distress. The training will cover how to recognize need for referrals and provide motivational interviewing and culturally sensitive assessment skills. To ensure quality control, the study coordinator will conduct refresher training for staff to ensure operating procedures are followed consistently. We will also develop checklists for tests requiring multiple tests as well as the use of tablet based tests to ensure quality assessments.

e. Aim 3

i. **Study design**

This Aim of the study involves 2 cross-sectional components:

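### The adjusted HEU vs HUU models condition on birthweight, preterm birth and LAZ, which follow the fetal exposure, so no confounder-adjusted total effect is planned

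*Protocol*

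**What the plan says.** The target is set in section 11, Aim 1a: whether fetal HIV/ART exposure affects 4-year neurodevelopment, and the influence of ART regimen and timing. No direct-effect or mediation aim is stated.

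The pathway is in section 8 (Background). It reports that "There is consistent evidence of lower birthweight and poorer growth in HEU compared to HUU". It also cites a sibling study linking higher birthweight to lower risk of several psychiatric conditions, and concludes that "it is plausible that HEU may have poorer neurodevelopmental and mental health outcomes via fetal exposure to HIV, ART, poor fetal growth". The same sentence adds stress and depression of the mother during pregnancy to these routes.

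The adjustment sets are in three places:
- Section 12.c.vii, opening paragraph, for all Aim 1 analyses, where the a priori list reads: "cofactors of interest in the multivariate analysis include household sociodemographic factors, birthweight, preterm birth, maternal depression, infant sex, maternal education, and infant/child LAZ". The next sentence sets the entry rule: "multivariate models will include non-collinear variables associated with growth in univariate model" at p < 0.05.
- Section 12.c.vii, Analysis paragraph (MDAT, ASD, SDQ): "Multivariate analyses will be adjusted for maternal sociodemographic factors and depression and infant birthweight and growth". No entry condition is attached.
- Section 12.d.vii (Aim 2): "potential confounders - maternal depression, preterm birth, and infant birthweight - in multivariate analysis", subject to a collinearity check.

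The Growth outcomes paragraph of section 12.c.vii makes WAZ, WHZ and LAZ each the outcome of univariate and multivariate mixed models. Univariate as well as multivariate regressions are also planned for MDAT and SDQ.

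**The concern.** A confounder must not be a consequence of the exposure. In Aim 1, section 16 says that all HEU mothers started ART before or during pregnancy, so preterm birth, birthweight and later LAZ come after exposure begins. The protocol itself describes fetal growth as something through which exposure may act.

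Conditioning on such variables removes the part of the effect that runs through them. It can also open a non-causal path through unmeasured shared causes of birthweight and development. The adjusted coefficient then answers a different question from the aim.

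This touches the primary outcome (MDAT, Table 6). The Background hopes for reassuring data, and the results go to policy makers under Aim 3. A small adjusted difference could be read as absence of harm when part of the harm had been adjusted away.

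**Working it through.** **1. The protocol's own figures.** Inputs from section 12.d.vii: SD 1.0 or 1.4, 80% power, alpha 0.05 (two-sided assumed), 1000 per group, or 800 after 20% attrition. Detectable difference = SD × (1.960 + 0.842) × √(2/n).
- n = 1000: 0.125 and 0.175, stated as 0.13 and 0.18.
- n = 800: 0.140 and 0.196, stated as 0.14 and 0.20.

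These reproduce. They are unadjusted two-group figures, so the adjustment set does not alter them.

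**2. What adjustment removes.** Let *a* be the HEU deficit in a growth variable (SD units) and *b* the slope of MDAT on it. In a linear model, adjusted effect = total − a × b. Residual SD is √(1 − b²), and the variance of the exposure coefficient is inflated by 1 + a²/4. Power = Φ(effect / [√(1 − b²) × √(1 + a²/4) × √(2/800)] − 1.96).

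The documents give neither *a* nor *b*. Assumed ranges: a = 0.1 to 0.4, b = 0.1 to 0.3. For a total of 0.14 SD (power 80% without the mediator):

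| a | b | Adjusted effect | Share removed | Power |
|---|---|---|---|---|
| 0.1 | 0.1 | 0.14 − 0.01 = 0.13 | 7% | 74% |
| 0.2 | 0.2 | 0.14 − 0.04 = 0.10 | 29% | 53% |
| 0.3 | 0.3 | 0.14 − 0.09 = 0.05 | 64% | 18% |
| 0.4 | 0.3 | 0.14 − 0.12 = 0.02 | 86% | 6% |

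For a total of 0.20 SD over the same ranges, 5% to 60% is removed and power goes from 98% to between 97% and 38%. For 0.30 SD, 3% to 40% is removed and power stays at 96% or more, but the estimate is still not the total effect.

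**3. Collider bias.** Assume a direct effect of −0.09, a birthweight deficit of 0.3 and a slope of 0.17. The total is −0.09 − 0.3 × 0.17 = −0.141. Add an unmeasured cause with coefficient *c* on birthweight and *d* on outcome, all variables on a unit scale. Adjusting for birthweight then gives −0.09 + 0.3 × c × d.
- c = d = 0.3: −0.063.
- c = d = 0.5: −0.015 (simulation: −0.018).
- c = 0.5, d = −0.5: −0.165, further from zero than the total.

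The direction therefore depends on signs that the documents do not give.

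**4. Growth models.** Illustrative coefficients: enrolment LAZ is lower by 0.3 in HEU, and 12-month LAZ = 0.6 × enrolment LAZ − 0.05 for HEU. The total 12-month difference is −0.05 − 0.6 × 0.3 = −0.23. Adjusting for enrolment LAZ leaves −0.05; same-visit LAZ leaves exactly 0. With WAZ = 0.7 × LAZ − 0.05 for HEU, the total of −0.05 − 0.7 × 0.23 = −0.21 becomes −0.05 given same-visit LAZ.

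**5. The entry rule.** Screening on association with growth readily admits birthweight, preterm birth and LAZ. It can drop a socioeconomic confounder of neurodevelopment that is unrelated to growth. For non-growth outcomes, it selects on the wrong variable.

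**The case against.** Several points on the other side stand.

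- Not every model contains all three variables. Entry under the opening paragraph is conditional, the MDAT/ASD/SDQ sentence omits preterm birth, and the Aim 2 list omits LAZ.
- A reader might infer that LAZ is measured at the same visit, so that growth is regressed on itself and its exposure effect is meaningless. The protocol gives no time point for LAZ, and no growth model is written with LAZ on both sides. That reading follows only from taking the words on all analyses literally. With enrolment LAZ it would be a baseline-adjusted model, which still removes part of the effect.
- A reader might also infer that bias toward zero is certain. Attenuation is expected when direct and indirect effects share a sign, but step 3 shows that it is not guaranteed.
- Univariate contrasts are planned, and HUU come from the same clinics. An estimate free of the growth variables will therefore exist.
- Covariate lists per model may be refined in an analysis plan that is not shown.

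The last two points do not dispose of the matter. Section 16 says only that shared recruitment attenuates confounding, and the team's own preliminary HEU deficits (Table 3) were adjusted for caregiver education, rent and food security. The protocol also does more than leave the covariates open: it names them, and for Aim 2 labels two of them confounders. A birthweight-adjusted model is legitimate as a secondary analysis, since birthweight may share causes with the outcome.

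**Conclusion.** The concern holds in limited form, as a should-fix. The protocol places in its adjustment sets variables that follow the exposure, and it describes fetal growth as an intermediate. Every described contrast is either unadjusted or open to conditioning on these variables, so no confounder-adjusted estimate of the total effect is planned.

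The likely consequence is attenuation, of unknown size. The 7% to 86% range rests entirely on assumed mediator strengths, a single linear mediator and a total effect of 0.14 SD. It shows sensitivity and is not an estimate. The LAZ covariate in growth-outcome models is an ambiguity to close, not a demonstrated error. Alpha, sample size and stated detectable differences are unaffected.

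**What to change.** - **Main adjusted model**, for HEU vs HUU and for ART timing and regimen: site, household sociodemographic factors, maternal education and infant sex. Infant sex is there for precision, not as a confounder.
- **Maternal depression:** state and justify its role. The Background lists depression in pregnancy among the possible routes, while PHQ-9 is first taken at enrolment, after birth. It belongs in the main model if it precedes exposure or shares causes with it, and otherwise in the secondary model.
- **Secondary model**, labelled direct effect or mediation: add birthweight, preterm birth and LAZ, with the LAZ time point named.
- **Growth outcomes:** exclude LAZ as a covariate.
- **Entry rule:** drop the p < 0.05 association-with-growth screen for non-growth outcomes.
- **Aim 2:** apply the same split, and stop calling birthweight and preterm birth confounders.

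The cost is protocol wording and one more model on data already being collected. The main model loses some of the residual-variance reduction that birthweight and LAZ would give.

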Design	
This study will provide rigorous epidemiologic evidence regarding the influence of fetal exposure to HIV and ART on developmental and mental health outcomes from infancy to adolescence using the following study designs: Longitudinal cohort study, cross sectional assessments and costing and implementation surveys. Accrued data will be disseminated in a stakeholder workshop conducted in the last year of the study.
 
To do this we will enroll a longitudinal cohort of HIV exposed uninfected (HEU) and HIV uninfected (HUU) infants and follow them up 6 monthly with extended follow-up to 4 years. Assessments will include growth, hearing and neurodevelopment (Aim 1a) and telomere length (Aim 1b).
 
In Aim 2, we will utilize a cross-sectional study design to pilot test mobile screening strategies to detect neurodevelopmental and mental health outcomes in HEU (Aim 2a). Pilot results will inform the implementation of a larger population based cross-sectional assessment of HEU outcomes (Aim 2b).
 
In aim 3, we will estimate the cost of the screening strategies and convene a stakeholder workshop to review data regarding programmatic integration of HEU screening.

Population	
Aim 1: HEU and HUU infants age 6 weeks and their mothers
 
Aim 2: HEU and HUU children and adolescents age 3-18 years and their caregivers
 
Aim 3: Abstracted records of cost information, Stakeholders in pediatric and adolescent health, health care workers (HCW), policy makers

Sample size	
Aim 1: 2000 mother-infant pairs, 1000 HEU and 1000 HUU
 
Aim 2: Pilot phase: 200 HEU and 200 HUU and their caregivers, Population based assessments: 4000 caregiver-child HEU pairs, 400 caregiver-child HUU pairs
 
Aim 3: 25-50 HCW, policy makers and stakeholders in pediatric health

Study sites:	
Aim 1: 5 public sector maternal and child health (MCH) clinics, 2 in urban Nairobi (Mathare, Kenyatta National Hospital) and 3 rural MCH clinic sites (Homa Bay, Kisumu, and Rachuonyo).
 
Aim 2: Pilot phase: Rachuonyo sub-county hospital. Population based assessments: 100 large HIV care clinics throughout Kenya
 
Aim 3: Workshop will be concerned in Nairobi/Western Kenya

Study Duration:	5 Years

8. Background

Maternal HIV and antiretroviral exposure may be potential fetal determinants of mental health

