Kenyatta National Hospital & University of Nairobi: Study participants for aim 1 will be recruited, and followed up clinics in Nairobi and Western Kenya. Cross-sectional surveys (Aim 2) will be done in various sites across the country. Kenyatta National Hospital and University of Nairobi collaborators will participate in study design, data analysis and interpretation, and manuscript preparation. Specimens will be processed and stored at the University of Nairobi Pediatric Research Laboratory.

Population Justification: This study will be conducted in Kenyan children and adolescents age 6 weeks-18 years. HIV-exposed uninfected (HEU) populations are growing in Kenya, and there is need to understand health differences and the effect of maternal HIV status and treatment on long term outcomes.

b. Summary table

	Aim 1	Aim 2	Aim 3
Study design	Longitudinal cohort study	Cross-sectional assessments	Implementation surveys, stakeholder workshop
N	Aim 1: 2000 mother-infant pairs: 1000 HEU and 1000 HUU	Aim 2: 4800 children and adolescents and their caregivers	Aim 3: 25-50 HCW, policy makers, stakeholders in pediatric health
Intervention	None	None	None

Outcomes	Neurodevelopment assessment scores, hearing, growth, hospitalization, morbidity and mortality	Neurodevelopment assessment scores, mental health, hearing	Cost, feasibility of screening, referral options for HEU
Enrollment age range	Infants age 6 weeks	3-18 years	>18 years
Health status	HEU, HUU infants	HEU, HUU children and adolescents	NA
Clinical Site	Nairobi, Western Kenya	Multiple sites in the country	NA
Study follow-up	6 weeks to age 4	NA	NA
Specimens	Dried blood spot	Dried blood spot	NA
Specimen collection timeline	Enrollment, yearly	Enrollment	NA
Use of specimens	Telomere length	Telomere length	NA

c. Aim 1

i. **Study design**

Longitudinal cohort study

ii. **Study populations**

2000 HEU and HUU infant-mother pairs enrolled at 6 weeks of age

iii. **Recruitment procedures**

Recruitment of participants

1000 mothers living with HIV (MLHIV) and 1000 HIV-uninfected mothers will be recruited with their infants (HEU and HUU) at 6 weeks during routine postnatal care at 5 MCH clinics (2 in Nairobi, 3 in Western Kenya). Clinic staff will be aware of the study and asked to identify potentially eligible mother-infant pairs and refer them to study nurse. A standard recruitment script will be used for recruitment. A recruitment log will be used to document reasons for declining to participate.

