Neurodevelopmental outcomes: MDAT scores (social, fine motor, gross motor, and language) will be analyzed as z-scores and descriptive statistics for each domain will be summarized and compared between HEU and HUU using linear regression, with clustering for site (Table 6). MDAT scores at baseline (6 weeks) and changes in MDAT scores during follow-up will be compared between HEU and HUU and among HEU by maternal VL detection in pregnancy, and by pre-conception versus later ART, and ART regimen (EFZ versus DTG-backbone) using univariate and multivariate linear regression. Prevalence of high risk for **ASD** as assessed by M-CHAT R/F and **hearing loss** will be compared for HEU and HUU using multivariate generalized linear models (GLM) with log link and binomial family for relative risk estimation, overall and stratified in HEU and HUU.

Table 6. Outcomes and analytic approach for longitudinal cohort		
Outcome variable	Comparisons	Analytic approach
Primary outcome: Neurodevelopmental outcomes MDAT	HEU vs. HUU Maternal VL Pre-conception ART EFZ vs. DTG	Linear regression for social, gross motor, fine motor, and language z-score GLM
ASD prevalence or hearing loss		
Secondary outcomes		
Growth (WAZ, WHZ, HAZ, HC at 12, 24, 48 months) Prevalence of underweight, wasting and stunting Growth trajectory (change in HAZ)	HEU vs. HUU Pre-conception ART EFZ vs. DTG	Linear mixed effects models
Hospitalization	HEU vs. HUU	Cox regression
Severe infections	HEU vs. HUU	Cox regression
Mortality	HEU vs. HUU	Cox regression

Growth outcomes: We will compare growth outcomes between HEU and HUU and among HEU by maternal VL detection in pregnancy, maternal pre-conception ART, and by ART regimen. Growth will be converted to z-scores using WHO Anthro software and 12- 24- and 48-month median WAZ, WHZ, and LAZ and prevalence of underweight, stunting and wasting will be compared. In addition, growth trajectory will be compared. Missing values will be imputed using Markov chain Monte Carlo procedures. Loess curves will be created to plot growth trajectory over time for WAZ, WHZ, and LAZ. Linear mixed-effects models will be used to determine correlates of growth (separately for WAZ, WHZ, and LAZ) in univariate and multivariate models.

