Cognitive outcomes. Cognitive assessments will be done using NIH Toolbox. The battery will include the tests Dimensional Change Card Sort Test, Flanker Inhibitory Control and Attention Test, List Sorting Working Memory Test, Pattern Comparison Processing Speed Test, and Picture Sequence Memory Test, which evaluate working memory, attention, processing speed, and other aspects of executive functioning. The NIH Toolbox has been validated for US children and was recently adapted through a rigorous process involving translation and backtranslation for Kenya, including translation to Dholuo and Kiswahili.

The table below summarizes the tools, age-group they are used in, screening time and domains or disorders they test.

Tool	Age-group	Time (minutes)	Types	Domains/Disorder
MDAT	0.6-5	30	Screening	Gross motor, fine motor, language, social
HearScreen TM	3+	5	Screening	Hearing
NIH Toolbox	6-17	25-30	Screening	working memory, attention, processing speed, executive functioning
Strengths and difficulties questionnaire (SDQ)	3-16 & caregivers	10	Screening	Emotional symptoms, conduct problems, hyperactivity/inattention, peer relationship problems
SNAP-IV	6-12	5-10	Screening	ADHD
PHQ-9	>16 & caregivers	3	Screening	Depression
MINI-KID	6-17	10	Diagnostic	Common psychiatric conditions
MINI	18	10	Diagnostic	Common psychiatric conditions
School performance	>10	1	NA	National exam results Parental report

vii. Sample size determination & data analysis

Effect size calculations: For comparisons of z-scores in MDAT or NIH-toolkit scores, we will be able to detect differences of 0.13-0.18 assuming a standard deviation of 1.0 or 1.4, 80% power and alpha of 0.05 in Aim 1 cohort (Table 10). In the cross-sectional cohort, 2- to 3-fold differences will be detectable, in diagnoses such as depression and ADHD. To detect smaller differences, more HUU could be enrolled in some age-strata based on pilot feasibility.

R61/R33 Aim 1 cohort	Effect detectable (no attrition)		Effect detectable (20% attrition)	Assumptions
Difference in z-score for MDAT	0.13 (SD=1.0)	1000 HEU:1000 HUU	0.14 (SD=1.0)	Standard deviation = 1.0-1.4 ¹⁰⁵
	0.18 (SD=1.4)		0.20 (SD=1.4)	
Difference in ASD prevalence	2.2%	1000 HEU:1000 HUU	2.5%	HUU ASD 2%
	3.3%	500 DTG: 500 EFZ	3.8%	
Difference in SDQ+ prev.	5.2%	1000 HEU:1000 HUU	5.9%	HUU SDQ+ 20%
	7.5%	500 DTG: 500 EFZ	8.5%	
Difference in hearing loss	1.7%	1000 HEU:1000 HUU	2.0%	HUU 1%
	2.7%	500 DTG: 500 EFZ	3.1%	
Difference in TL	0.18	500 HEU: 500 HUU		SD=1.0

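### The primary MDAT regression is clustered on only five sites, and on the natural reading that analysis cannot deliver both the 5% alpha and the 80% power stated for it

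*Protocol*

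**What the plan says.** Protocol section 12.c.vii, under Neurodevelopmental outcomes, has the MDAT domain z-scores "compared between HEU and HUU using linear regression, with clustering for site". It names no variance estimator, reference distribution or small-sample correction. Linear mixed models are named in the same section, but for growth and not for MDAT.

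The synopsis places Aim 1 in "5 public sector maternal and child health (MCH) clinics", and the recruitment text in section 12.c.iii also gives five. Enrolment is "2000 mother-infant pairs, 1000 HEU and 1000 HUU". That ratio is set overall; no ratio or quota is set within a site.

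The effect size paragraph in section 12.d.vii claims detectable "differences of 0.13-0.18 assuming a standard deviation of 1.0 or 1.4", with "80% power and alpha of 0.05 in Aim 1 cohort". With 20% attrition its table gives 0.14 (SD 1.0) and 0.20 (SD 1.4).

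The list of a priori cofactors in section 12.c.vii does not name site. Section 16 says HUU infants come from the same clinics as HEU infants, as a guard against confounding.

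**The concern.** A cluster-robust variance is estimated from the variation between cluster totals, so its precision depends on the number of clusters and not on the number of infants. Five sites leave about 4 degrees of freedom for the primary contrast. The analyst must then either use 1.96 and over-reject, or use the t critical value of 2.776 and lose power. In neither case do the alpha and power in the effect size table both describe the analysis in section 12.c.vii.

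The second issue is the estimate itself. Clustering changes the standard error and leaves the HEU minus HUU difference as it was. Recruiting both groups at the same clinics guards fully against confounding by clinic only if the HEU:HUU ratio is the same at each clinic or the model conditions on clinic. The protocol fixes neither.

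**Working it through.** **Inputs.** From the protocol: 1000:1000, or 800:800 after 20% attrition; SD 1.0 or 1.4; alpha 0.05, taken as two-sided; power 80%; five sites. Not given and therefore assumed where used: site variance, site sizes and the ratio within each site.

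**1. Reproduce the printed figures.** Two independent samples, no cluster term: difference = (1.960 + 0.842) × SD × √(2/n).

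- n = 1000: √(2/1000) = 0.0447, giving 0.125 (SD 1.0) and 0.175 (SD 1.4).
- n = 800: √(2/800) = 0.0500, giving 0.140 and 0.196.

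These round to the printed 0.13, 0.18, 0.14 and 0.20. The table therefore makes no allowance for clustering.

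**2. Five-cluster robust standard error with a normal reference.** Size = P(|t₄| > 1.96) = 12.2%. Simulation (least squares, sandwich variance with the G/(G−1) correction, 8000 runs per setting, each site 1:1) gave 11.5% to 13.4%.

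**3. The same standard error with t on 4 df.** The critical value is 2.776, which is 1.42 times 1.96. Power comes from a noncentral t with 4 df and noncentrality difference / (SD × √(2/n)).

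- At 0.125 SD: noncentrality 2.80, power 56.4% (simulated 56% to 58%).
- At the printed 0.13: noncentrality 0.13/0.0447 = 2.91, power 59.4%.

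Power of 80% needs a noncentrality of 3.761, so the detectable difference is 3.761 × SD × √(2/n):

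| n per group | SD | Printed | With t on 4 df |
|---|---|---|---|
| 1000 | 1.0 | 0.13 | 0.168 |
| 1000 | 1.4 | 0.18 | 0.235 |
| 800 | 1.0 | 0.14 | 0.188 |
| 800 | 1.4 | 0.20 | 0.263 |

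**4. Site as a fixed effect, ordinary standard errors.** Residual df are 2000 − 6 = 1994. Size is 5% and power at 0.125 SD is 80.0% when each site is 1:1.

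**5. If the HEU:HUU ratio differs by site (assumed layouts, site SD 0.2 to 0.316).** Clustered t(4) power in simulation was 47% to 52% with mild imbalance (HEU:HUU from 230:170 to 170:230 across sites) and 29% to 40% with strong imbalance (from 300:150 to 100:200).

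**6. Possible bias (assumed illustration).** Bias = −(regional gap in mean score) × (western share of HEU − western share of HUU). With a gap of 0.2 SD and shares of 70% and 50%, bias = −0.2 × 0.20 = −0.04 SD. With shares of 80% and 40% it is −0.2 × 0.40 = −0.08 SD. If either the gap or the difference in shares is zero, there is no bias.

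**The case against.** The strongest objection is that the estimator is assumed. The protocol names none, and a random intercept or site indicators with model-based errors would keep size and power near 5% and 80%. This stands as a limit. The robust reading is still the natural one, because the protocol names mixed models where it intends them.

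A reader might infer that the primary p-values and confidence intervals will be wrong. The document does not support that. With t on 4 df, the usual reference for clustered linear regression, and balanced sites, they are valid and only precision is lost. The 12% and the 56% are alternatives and cannot both occur.

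A reader might also infer that every Aim 1 model is affected. Within Aim 1, clustering is stated only for the MDAT linear regression; the text on the GLM, growth, Cox and SDQ logistic models does not mention it.

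Confounding by site might be read as shown. It is not. It needs both the HEU:HUU ratio and mean MDAT to vary by site, and the protocol reports neither. Recruiting HUU at the same clinics makes it less likely.

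The loss matters less if the true difference is large. With t on 4 df, power at 0.2 (SD 1.0) is 91%, or 84% after 20% attrition. With SD 1.4 and no attrition it is 67%. This does not rescue the printed figures.

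Finally, fixed effects have a price. If the HEU effect itself varies between sites, ordinary standard errors are too small for an average over a wider set of clinics. Adding a between-site variance τ²/5 to 2/1000 gives rejection rates of about 8% at τ = 0.05 and about 17% at τ = 0.1 (both values assumed), while t(4) stays near 5%. Section 16 describes Aim 1 as population-based, so the target of inference needs stating. This caveat stands.

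**Conclusion.** The point holds for the primary MDAT regression, on the reading that clustering means cluster-robust errors over five sites. On that reading the stated alpha and power cannot both be true. Either the false-positive rate is about 12%, or power at the planned difference is 56% to 59% and the detectable differences are about a third larger than printed (3.761/2.802 = 1.34 before rounding). The printed power figures belong to an unclustered comparison.

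The size and power results assume equal HEU and HUU numbers within each site; an uneven ratio together with differing site means lowers power further. Confounding by site is a possibility that the planned method would not address, and nothing in the protocol shows that it exists.

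**What to change.** In the MDAT linear regression, replace the clustering phrase with site as a fixed effect (four indicators), using ordinary or individual-level heteroscedasticity-robust standard errors. Adding the indicators while keeping five-cluster robust errors would not solve the problem: simulated size with a normal reference stays at about 12% to 13%, and t(4) power at 54% to 59%. State that inference is conditional on these five clinics, and report the site-by-exposure interaction as a check on a common effect.

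If the team prefers site-clustered errors because it wants to generalise beyond these clinics, specify t on 4 df and restate the detectable differences as about 0.17 and 0.24, or 0.19 and 0.26 with 20% attrition.

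Site adjustment in the other Aim 1 models is optional, for consistency. Clustering in Aim 2, over about 100 clinics, can stay.

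The cost is a change of wording, four degrees of freedom out of roughly 2000, and an explicit limit on the population to which the primary result applies.
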